**Explanations of measurements and assessments:**

*Labs for exenatide and diet interventions:* The placebo of this study allows us to compare metabolic changes that occur with exenatide versus diet-induced weight loss. We are particularly interested in the 5% and 10% weight loss timepoints and will measure metabolic parameters when that degree of weight loss is achieved. However, the 5%, 10%, 15%, and > 15% weight loss metabolic visits will not be scheduled within 2 weeks of starting the treatment, as acute weight loss within this time frame is likely due to fluid shifts rather than fat loss.

*Bioelectrical impedance:* Bioelectric impedance analysis (BIA) measures the opposition of bodily tissues to the flow of a mild (less than one milliAmp) alternating electric current (Gudivaka et al., 1999). Impedance is a function of two components (vectors): the resistance of the tissues themselves and the additional opposition (reactance) due to the capacitant effect of membranes, tissue interfaces, and nonionic tissues. Electrodes are typically placed on a wrist and an ankle and change in voltage between electrodes is measured. RJL system Quantum II Bioelectrical Body Composition Analyzer Testing using Cyprus software will be used in this study. The subject is generally tested using the right arm and foot. She will be in a supine position with arms 30 degrees from the body and legs not touching. The testing time takes less than 2 minutes and results are immediately available from software program. Resistance and reactance are used to calculate % body fat (Kotler et al., 1996).

*Visual Analog Scales:* Visual analogue scales are used to measure subjective satiety and hunger (Cornier et al., 1994). Satiety will be defined as the sensation of fullness after eating so that a person does not feel the need to eat for some time afterward. Hunger will be defined as the subjective driving force for the search for, choice of, and ingestion of food. Subjects will be instructed to make a single vertical mark on a horizontal 10-cm bar to indicate their current feelings, ranging between "not hungry at all" and "really hungry", between "empty" and "full" and between "not at all nauseated" and "extremely nauseated." Subjects will complete the VAS the day prior to the study visit, once in the morning in the fasted state and a second time 2 hours after eating their evening meal. The visual analog packet will also include questions about eating habits, including overeating and binge eating. The entire packet will take less than 5 minutes to complete.

*Resting energy expenditure:* Indirect calorimetry calculates heat production by measuring gas exchange. During resting conditions, food sources are broken down to produce energy (heat or KCALS). The oxygen consumed and the carbon dioxide produced are measured to provide an indirect assessment of caloric expenditure. Resting energy expenditure (REE) provides the total energy expenditure in 24 hours and is calculated from the gas exchange data (VO2, VCO2) collected by the Vmax. When obtaining a subject's REE, the subject reaches a steady state condition, which is defined as five consecutive minutes in which the VO2 and VE are within 10% and the RQ (respiratory quotient) is within 5%. Subjects in the fasted state will lay face up on an examination bed for approximately 20-30 minutes with a mask over the nose and mouth while measurements of gas exchange are taken. The use of indirect calorimetry to measure REE has been used as a measure of energy expenditure in clinical studies with obese subjects (Perseghin, 2001; Smith et al., 2005).

*Mixed meal test:* After an overnight fast, subjects will consume a standardized liquid test meal containing 35% of their calculated 24-hour energy requirements distributed as 40% of total calories from fat, 40% from carbohydrate, and 20% from protein. After the meal, serum insulin and triglyceride levels will be measured.

*Physical activity monitoring with actigraph watches:* If the device is available, subjects will be given actigraph monitors at week 0 to measure baseline physical activity levels. The will allow us to compare and control for baseline physical activity level differences between the placebo and exenatide groups. Subjects will be asked to wear the monitors again at week 12, at week 24, and after achieving 5%, 10%, 15%, and > 15% weight loss.

*Thermic effect of food:* Immediately after the mixed meal is consumed, subjects will remain supine for 4 hours while energy expenditure is measured using indirect calorimetry. Resting energy expenditure will be measured for 15-20 minutes every hour for four hours in a subset of subjects. Blood will be drawn between these REE measurements.

*Laboratory studies:*

- Analysis of the CBC, standard chemistries, lipid panel, transaminases (AST and ALT), lipase, TSH, and hemoglobin A1c will be performed at LabCorp.

- Analysis of leptin, insulin, cortisol, adiponectin, and CRP will be performed at the Harvard Catalyst Core Laboratory (HCCL). CRP may be analyzed at LabCorp as well.
- Analysis of soluble leptin receptor and FGF21 will be performed in the laboratory of **[name]** using commercially available ELISA kits.
- Blood will also be banked at enrollment (week 0), week 12, week 24, week 52, 5% weight loss, 10% weight loss, 15% weight loss, and > 15% weight loss in 5% increments for future measurement of incretin levels or other proteins or hormones involved in metabolism. The banked blood may be analyzed in the HCCL, the laboratory of **[name]**, or in collaboration with other researchers.

## **B. Statistical Considerations**

### *Statistical methods:*

For the first objective of this study, we will examine the patterns of weight loss (termed “trajectories”) for the subjects with robust weight loss in the exenatide group (A), and also those in diet-induced weight loss group (B). We expect to see that in group A, the trajectory of weight loss for the majority of subjects will be consisted of 2 linear segments (T1). The first segment starting at week 12 will have a steeper negative slope (rate of weight loss decrease) than that of the second linear segment, which would have a less steep slope and plateau out toward week 52. However, individual subjects are expected to follow different trajectories. For example, some may have a constant gradual negative slope from week 12 to week 52 (one single linear segment), some may have three segments (plateau at first, then decrease, then plateau), and some may have no change at all after week 12 (one single plateau). The trajectory analysis will allow us to first assess the number of possible trajectories, and second, the shapes of the trajectories of weight loss. We are most interested in trajectory T1 which would allow us to estimate not just the rate of change over time for each of the two linear segments, but also the duration of time for each of the two segments.

To estimate the number and shape of the weight loss trajectories, we will use a mixture modeling technique of the longitudinal data of monthly weights for each subject. We will first plot the data for each subject over time. The graphs will allow us to have some understanding of the shape of the observed trajectories, and how the curves cluster. We will assume that the number of clusters ranges from one to six, but we expect the optimal estimate of the number of clusters is three or four, as described above, with the largest cluster consisting of trajectory of shape T1. The marginal density of a subject having weight measurement at a particular time point is modeled as a function of the product of two densities: the probability of the weight measurement belonging to a particular group, and the probability of observing such a measurement conditioning on the particular group. The first probability is modeled using a generalized logit model since the outcome is categorical (from 1 to 6 categories/types of trajectories), and the second probability is a polynomial linear regression of the weight measurement as a function of time (linear, quadratic, cubic). To select the optimal number of trajectories, we will compare the Bayesian Information Criteria (BIC) value from the six models (corresponding to 1 to 6 types of trajectories). The algorithm and the SAS macro for this type of modeling has been published (Jones 2007). We will repeat the modeling technique above for group B in order to assess the number and shapes of the trajectories in this group.

For aim 2, we will first create a binary outcome variable. The outcome is 1 if the weight loss difference between 12-week and 52-week is at least 1 kg; otherwise, it is 0. We will perform multivariable logistic regression to assess the association between metabolic parameters and this outcome. We consider the association to be statistically significant if the p-value is less than 0.05, and the overall model c-statistic is above 0.8. Once these metabolic parameters have been identified and quantified, we will also use the result from the trajectory analysis (aim 1) to assess the distribution of the metabolic parameters across different trajectories. We will model the likelihood of falling into a particular trajectory as a function of metabolic parameters (i.e. the change in a particular metabolic parameter may affect a certain trajectory but not all trajectories of weight loss).

We will repeat these models for the subjects in group B. The difference in the estimates of the model coefficients between the two groups (A and B) implies the potential effect of exenatide.

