- **Weeks 16 and 20 — Follow-up visits**
  - Standard measurements
  - Dietary counseling
  - VAS for nausea, satiety, hunger
  - 24-hr food recall
  - Assessment of symptoms, adverse events, and diet/medication compliance
  - If subject has attained 10%, 15%, or > 15% weight loss in a 5% increment, follow 10% weight loss procedures”
  - Urine pregnancy test for premenopausal women
  
- **Week 24 — Follow-up visit with safety labs; discontinue <10% weight loss on placebo**
  - Fasting safety labs (CBC, metabolic panel, transaminases, lipid panel, lipase)
  - Fasting leptin, soluble leptin receptor, insulin, cortisol, adiponectin, CRP, FGF21 levels
  - Physical exam
  - Standard measurements
  - Dietary counseling
  - VAS for nausea, satiety, hunger
  - 24-hr food recall
  - Assessment of symptoms, adverse events, and diet/medication compliance
  - Resting energy expenditure
  - Mixed meal test
  - Thermic effect of food (TEF) in subset of subjects
  - Subjects who have not lost 10% body weight on placebo treatment discontinue participation at 24 weeks
  - Physical activity monitoring in subjects continuing participation if device is available
  - Urine pregnancy test for premenopausal women
  
- **Weeks 28, 32, 36, 40, 44, 48 — Followup visits**
  - Standard measurements
  - Dietary counseling
  - VAS for nausea, satiety, hunger
  - 24-hr food recall
  - Assessment of symptoms, adverse events, and diet/medication compliance
  - If subject has attained 10%, 15%, or > 15% weight loss in a 5% increment, follow 10% weight loss procedures”
  - Urine pregnancy test for premenopausal women
  
- **Week — 52 Final Treatment visit**
  - **Discontinue exenatide treatment or placebo intervention**
  - Fasting safety labs (CBC, metabolic panel, transaminases, lipid panel, lipase)
  - Fasting leptin, soluble leptin receptor, insulin, cortisol, adiponectin, CRP, FGF21 levels
  - Physical exam
  - Standard measurements
  - VAS for nausea, satiety, hunger
  - 24-hr food recall
  - Assessment of symptoms, adverse events, and diet/medication compliance
  - Resting energy expenditure

- Mixed meal test
- Thermic effect of food (TEF) in subset of subjects
- Urine pregnancy test for premenopausal women
- **1, 3, and 6 month follow-up visits**
  - Standard measurements
- **5% Weight Loss Procedures**
  - Fasting lipid panel
  - Fasting leptin, soluble leptin receptor, insulin, cortisol, adiponectin, CRP, FGF21 levels
  - Standard measurements
  - VAS for nausea, satiety, hunger

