**Sample size calculation:**

Based on published literature describing weight loss with exenatide treatment among individuals with type 2 diabetes, we hypothesize that responders will stratify into a plateau group and a continued weight loss group by 52 weeks of treatment. The sample size is based on the difference between two differences of weight. The first difference is the weight difference between week 12 and week 52 for the exenatide group (group A), and the second difference is the difference between week 12 and week 52 for the diet-induced group (group B). The difference in weight loss between these two groups is hypothesized to be 1 kg (i.e. the exenatide group between week 12 and 52 loses on the average 1 kg more than group B). The common standard deviation of the distribution of the weight loss difference is 1.2 kg. We plan to enroll 150 subjects in group A and 36 in group B. Given an expected dropout rate of 25% from the screening visit, we will screen 200 for group A, and 50 for group B. At 12 weeks, we expect that 30% of group A will be high responders (50 subjects). At 52 weeks, we expect the dropout rate to be 25% for group A and 50% for group B. Thus we will have 38 subjects left for group A, and 18 for group B for final data analysis. Given this sample size, we will still have a power of 0.83 to detect the difference of 1kg.

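### Read literally, the trajectory mixture is fitted to raw monthly weights with no subject-level term, so its classes would follow body size; on any outcome scale, no estimator is given for the T1 segment durations

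*Combined protocol and SAP*

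**What the plan says.** Section B3.B, Statistical methods, sets the target as patterns of weight loss from week 12 to week 52 in exenatide responders (group A) and in the diet group (group B). It describes four shapes: two linear segments (T1), one steady decline, a three-part course ("some may have three segments (plateau at first, then decrease, then plateau") and a flat line. T1 is of most interest because it is meant to yield each segment's rate of change, "but also the duration of time for each of the two segments".

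The model comes next: "we will use a mixture modeling technique of the longitudinal data of monthly weights for each subject". Class membership follows a generalized logit, and "the second probability is a polynomial linear regression of the weight measurement as a function of time (linear, quadratic, cubic"). BIC chooses among one to six classes; "we expect the optimal estimate of the number of clusters is three or four", with T1 the largest. The same modelling is repeated in group B. A published algorithm and SAS macro are cited without options.

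Nothing in Statistical methods mentions change or percent change, centring, a baseline covariate, a subject effect, a knot or a rule for reading off a duration.

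The Sample size section adds: "The common standard deviation of the distribution of the weight loss difference is 1.2 kg" and "At 52 weeks, we expect the dropout rate to be 25% for group A and 50% for group B", leaving 38 and 18 women. Under Study Visits, Week 24: "Subjects who have not lost 10% body weight on placebo treatment discontinue participation at 24 weeks".

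**The concern.** There are two separate problems.

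**Outcome scale.** A mixture of class curves with no subject term must explain every difference between women by class. If the outcome is weight in kg, the largest difference is how heavy each woman is. Classes then become weight bands, and the shapes of interest are lost.

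**Duration.** A polynomial bends gradually and has no parameter for the time at which one segment ends. The promised segment durations therefore have no defined estimator, whatever the outcome scale.

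This is the stated analysis for the second primary objective in B1 (long-term patterns of weight loss), which Statistical methods calls the first objective. Class membership is later modelled on metabolic parameters, so any marker that tracks body size could look like a predictor of trajectory.

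**Working it through.** **The plan's own figure.** With 38 and 18 women, SD 1.2 kg and a 1 kg difference: SE = 1.2 × √(1/38 + 1/18) = 0.343; 1/0.343 = 2.912; power = Φ(2.912 − 1.960) = 0.83 (two-sided 0.05 assumed). The stated 0.83 is reproduced. It concerns a difference in mean change, not the trajectory model.

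**Size against change.** BMI 28-50 at an assumed height of 1.63 m gives 28 × 1.63² = 74 kg to 50 × 1.63² = 133 kg. The plan gives no between-woman SD, so 8 to 15 kg is assumed. Ratio of variance in level to variance in change: (8/1.2)² = 44 to (15/1.2)² = 156.

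**Simulation of the model as written.** Cubic class curves, common variance, 1-6 classes, BIC, 11 visits at weeks 12-52. Assumptions: mean week-0 weight 95 kg; the four shapes in shares 50/20/15/15%; visit noise 0.8%; later loss of 2.5, 5 or 10%; either 38 completers, or 50 or 90 women with 25% dropout. The 50 is the plan's number of week-12 responders; 90 = 150 × 60%, using the response rate reported under Rationale for study design. Adjusted Rand is 0 for chance agreement with the true shape and 1 for perfect agreement.

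Raw kg, SD 8 or 15 kg: six classes in 1792 of 1800 runs; class explained 88-97% of week-12 weight variance; Rand 0.00-0.05. A second set of simulations (losses of 3 or 8 kg, SD 8-16 kg, 38 or 50 women) agreed: six classes every time, 91-97% of variance, Rand about zero. Even at an implausibly narrow SD of 3 kg, class explained 81-93%.

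**Alternative outcomes** (results for later loss 2.5/5/10%):

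| Outcome and setting | Mean classes | Rand |
|---|---|---|
| Percent weight, subject intercept, 38 completers | 2.4/3.6/4.0 | 0.35/0.85/1.00 |
| Same, 50 women with dropout | 2.4/3.6/4.0 | 0.28/0.78/0.94 |
| Same, 90 women with dropout | 2.7/3.9/4.0 | 0.37/0.81/0.94 |
| Minus observed week-12 weight, 38 completers | 4.4/5.6/5.9 | 0.19/0.45/0.66 |
| Weight alone centred, 50 with dropout | 2.4/3.8/5.5 | 0.28/0.67/0.74 |
| Subject intercept in kg, 50 with dropout | 2.4/3.7/4.8 | 0.26/0.73/0.77 |
| Percent weight, subject intercept, 50 women who vary within a shape | 2.6/5.0/6.0 | 0.13/0.33/0.38 |

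The last row assumes a pace SD of 30% and a break SD of 4 weeks. With a subject intercept on percent weight (first three rows), class explained 2-9% of weight variance.

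**Reading a break from a polynomial.** Take a noise-free T1 curve falling 0.30% per week to week 28, then flat. The fitted slope reaches zero at week 40 (cubic) or 41 (quadratic), but lies midway between the two true slopes at week 27 or 29. That is a gap of 13 or 12 weeks for the same curve. The cubic's inflection falls at weeks 37, 48 and 16 for true breaks at weeks 20, 28 and 36.

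**Change-point alternative.** Fitted to the largest estimated class (50 women, dropout), the break had 95% simulation ranges of 19.5-43.1, 26.0-30.1 and 27.4-28.5 weeks. With T1 membership known they were 25.5-31.0, 26.5-29.5 and 27.5-28.5. Treating classes as known therefore overstates precision most when later loss is small.

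**Group B.** The largest model allowed has 6 × 4 curve coefficients + 5 class probabilities + 1 variance = 30 parameters, beside 18 women expected at week 52.

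**The case against.** **The text can be read as change.** The stated target is weight loss, every shape described is a course from week 12, and monthly weights may only name the source data. This stands in part. A reader might infer that the plan certainly models raw kg; the documents do not settle that. They equally do not define the outcome as change, and the table shows that the kind of change chosen matters.

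**The failure would be noticed.** Individual plots come first, and six weight bands would contradict the expected three or four classes. This is fair, but the plan names no fallback, so the outcome would be redefined after seeing the data.

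**The remedy looks better than it is.** This stands. Only the 2.5% case, with an SD of change of about 1.3-1.4 kg, fits the plan's 1.2 kg; 5% and 10% imply about 2.1 and 3.7 kg. Within-shape variation lowers recovery further, and at 10% loss it brings six classes back.

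**Polynomials carry timing information.** The slope midpoint lies close to a break at week 28. However, that reading presumes the two slopes are known, and the plan states no such rule.

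**Group B can be overstated.** It is tempting to say that a woman leaving at week 24, with weights at weeks 12, 16, 20 and 24, cannot support a cubic. That does not follow, because class curves pool all women in a class. Nor is 30 parameters the expected fit: it is the ceiling, and BIC may choose fewer classes. The 18 are week-52 completers, so week-24 leavers are not among them.

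**Conclusion.** The point holds and should be fixed. As worded, the model would classify by body size under every between-woman SD tried from 8 to 16 kg. That result depends on taking the outcome literally as weight in kg and on the assumed SDs, shape mix and noise. The duration gap needs none of these assumptions: the promised quantity has no estimator, and plausible readings of one curve differ by more than ten weeks.

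The reach is limited. A reader might infer that the powered comparison or the main aim 2 analysis fails as well. Neither does: the 0.83 concerns mean change between groups, and aim 2's binary 1 kg outcome does not use the classes. Only the later step that relates class membership to metabolic parameters inherits the problem.

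**What to change.** 1. State the outcome as percent weight (for example percent of week-0 weight) over weeks 12-52, with a subject intercept in the class curves. Centring both the weight and the time terms over each woman's attended visits is equivalent. Prefer this to subtracting the single observed week-12 weight, whose error carries into every later visit, and to centring weight alone when there is dropout.
2. Estimate the T1 slopes and segment durations with a piecewise-linear change-point model with a subject intercept, allowing zero, one or two knots. Take intervals from resampling women and repeating the classification in each resample.
3. In group B, report classes as descriptive with individual plots, and state that weeks 28-52 contain only women who met the week-24 criterion.

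The cost is SAP wording and different code on the same data, with no change to visits or conduct. The gain is limited: at later loss near 2.5%, expect two to three classes, Rand about 0.3-0.4 and a wide interval for the break. If women vary within a shape, recovery is about 0.1-0.4 even at larger loss, so classes need cautious reporting. Coverage of the resampling interval has not been simulated and should be checked before it is adopted.

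### BIC alone chooses among one to six trajectory classes with no within-class variation, fitted separately in about 38 and 18 women, so it is likely to report subgroups that do not exist

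*Combined protocol and SAP*

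**What the plan says.** Long-term patterns of weight loss are a primary objective (Primary Outcomes). Under Statistical methods, the most wanted pattern, T1, has two linear segments from week 12, and the plan wants the slope and the duration of each. The model proposed is a mixture fitted to each woman's monthly weights. On the number of classes: "We will assume that the number of clusters ranges from one to six", with three or four expected. Within a class the curve is a "polynomial linear regression of the weight measurement as a function of time (linear, quadratic, cubic"). Selection is by one rule: "we will compare the Bayesian Information Criteria (BIC) value from the six models (corresponding to 1 to 6 types of trajectories"). Then: "We will repeat the modeling technique above for group B in order to assess the number and shapes of the trajectories in this group".

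The section mentions no within-class random effects, minimum class size, stability check, lower cap for the smaller group, or choice between observations and subjects as the sample size in BIC.

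After the aim 2 models, the section closes: "The difference in the estimates of the model coefficients between the two groups (A and B) implies the potential effect of exenatide". The Sample size calculation gives the numbers: "We plan to enroll 150 subjects in group A and 36 in group B", "we expect the dropout rate to be 25% for group A and 50% for group B", and "Thus we will have 38 subjects left for group A, and 18 for group B for final data analysis".

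**The concern.** If every woman in a class is assumed to share one curve, with only independent error around it, then ordinary variation in starting weight or rate of loss has nowhere to go except into extra classes. BIC then rewards those classes because they do improve the fit, although no distinct subgroups lie behind them. On raw weight the problem is sharper: women enter with a BMI of 28 to 50, so classes would form by body size rather than by pattern of loss.

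At stake is a primary objective. The classes also feed aim 2, where membership is modelled on metabolic parameters. Spurious classes would carry through, and classes derived separately in each arm have no guaranteed counterpart in the other.

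**Working it through.** **The plan's own figures.** Group B: 36 × 0.5 = 18. Group A: 50 × 0.75 = 37.5, taken as 38. (The 50 is itself loose: 30% of 150 is 45, and 45 × 0.75 is about 34.) Power for a 1 kg difference with SD 1.2 kg, assuming two-sided 5%: 1 / (1.2 × √(1/38 + 1/18)) = 2.912; 2.912 − 1.960 = 0.952; Φ(0.952) = 0.83. This matches the stated power, but it covers a two-group mean difference, not the trajectory analysis.

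**Size of the mixture.** With a common residual SD, K cubic classes need 4K + (K − 1) + 1 = 5K parameters: 20 at K = 4 and 30 at K = 6. Linear classes need 2K + (K − 1) + 1 = 3K: 12 at K = 4. Visits at weeks 12, 16, ..., 52 number 11, so 18 women give 18 × 11 = 198 weights. Average women per class at K = 4 and K = 6 are 4.5 and 3 with 18 women, or 9 and 6 with 36.

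**Behaviour of BIC.** Data were simulated from one population with no classes, and the mixture was fitted for K = 1 to 6 with cubic classes (some rows also allowed linear). The 1.2 kg SD is the plan's; visit errors and the 12 kg between-woman SD are assumptions. Where 1.2 kg is read as the total SD of observed change, 1.2² = (slope SD)² + 2 × (error SD)². The rows marked *not subtracted* use a common known start; the *subtracted* row removes each woman's observed week 12 value. Results for n = 18:

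| Setting | BIC on observations | BIC on subjects |
|---|---|---|
| Identical women, independent error 0.8 kg | one class 100% | one class 100% |
| Raw weight, between-woman SD 12 kg | five or six classes 100% | five or six classes 100% |
| Change, week 12 subtracted, error 0.5-0.8 kg | three or more 38-98% | three or more 78-100% |
| Not subtracted, total SD 1.2, error 0.3 kg | three or more 100% | three or more 100% |
| Not subtracted, total SD 1.2, error 0.5 kg | three or more 56% | three or more 93% |
| Not subtracted, total SD 1.2, error 0.6 kg | three or more 40% | three or more 73% |
| Not subtracted, total SD 1.2, error 0.8 kg | one class 99% | one class 80% |

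The raw-weight result held even when all women had the same slope. In the 0.5 kg row, the smallest class held three women or fewer in 45% (observations) or 75% (subjects) of runs. With 60 data sets, the Monte Carlo SE is at most √(0.25/60), about 6.5 points.

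**Why the last row differs.** With error 0.8 kg, the slope SD is √(1.44 − 1.28) = 0.4 kg, so almost no variation between women remains to be split. Subtracting the observed week 12 value brings the classes back, because its error is shared by all of that woman's later values and acts as an unmodelled offset.

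**Larger n.** At n = 36 with BIC on subjects, three or more classes appeared in 100% of runs at 0.5 kg error (not subtracted), and six classes in 100% on raw weight. Identical women still gave one class in 97%.

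**T1.** A polynomial in time has no change point, so it does not return two slopes and two durations.

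**The case against.** Several stronger readings are tempting, and the documents do not support them.

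- *BIC gives no protection.* It does penalise classes, and it chose one class every time at n = 18 when women were identical. The failure comes from combining BIC with a model that has no within-class variation. It also depends on the noise: with slope SD 1.2 kg, error 1.0 kg and week 12 not subtracted, BIC on observations chose three or more classes in only 9% of runs.
- *The plan will report subgroups of two or three women that do not exist.* That is a likelihood, not a certainty. The simulations assume no subgroups, whereas the plan expects distinct shapes and may be right.
- *There are more parameters than women.* This holds for four or more cubic classes in 18 women, but cubic is the highest order listed and there are about 198 weights. Also, 18 is the week 52 count; nothing limits the fit to completers.
- *The arms cannot be compared at all.* Shapes can be compared descriptively, and description is the stated aim of the group B fit.
- *The closing sentence of Statistical methods fails for every model.* It follows the aim 2 paragraph and most naturally refers to those models. The logistic regression on the 1 kg outcome uses a fixed outcome, so its coefficients correspond across arms. Only the trajectory-membership model is affected, because its outcome categories come from classes derived separately.

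It is also fair to say that one piecewise model cannot count trajectories, and that a fixed class cap or minimum class size would be a matter of preference. The fix therefore keeps a mixture model and sets neither number.

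**Conclusion.** The concern holds in a limited form. As written, the rule is likely to report spurious classes whenever women differ continuously in weight or rate of loss. On raw weight, which is what the text describes, the result was five or six classes in every run under the assumed 12 kg spread. On change from week 12 the size is uncertain: about 38-98% or 78-100% of runs with three or more classes, according to how BIC counts its sample size, and little or no splitting in the most favourable case tried (most of the 1.2 kg being measurement error, and no subtraction of week 12). Raising the diet group from 18 towards 36 does not cure it.

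Two parts need no simulation. Polynomial classes do not estimate the quantities wanted for T1, and the plan has no rule for matching classes between arms, so class-based differences cannot carry an inference about exenatide. Confidence is medium, because visit error and between-woman spread are assumed and the documents give neither.

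**What to change.** 1. Analyse change, or percent change, from week 12 rather than raw weight.
2. Estimate T1 with one piecewise-linear mixed model in both groups together, using all available visits, with random intercepts and slopes, arm-by-segment terms, and adjustment for weight loss at week 12. The random intercept matters because subtraction alone does not remove the problem. This gives the slopes, the change point and a test of the arm difference. State its limit: under Overview and Study duration, only placebo women below 10% loss leave at week 24, while exenatide high responders stay through plateau or regain, so the arm contrast after week 24 is restricted.
3. Keep the mixture model as descriptive. Fit it once to both groups pooled, with within-class random effects and arm as a class-membership covariate. State which sample size BIC uses, and do not interpret classes holding only a few women.
4. Drop the separate mixture fit in group B, and use the pooled classes wherever aim 2 models trajectory membership.

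The cost is a rewrite of the analysis plan, with no new visits or data. The downside is that fewer and coarser patterns will be described in each arm.
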